## **STUDY INTERVENTION**

Our deprescribing protocol is based on a conceptual framework by Holmes that considers patient and disease factors, goals of care, appropriate treatment targets, and the duration of treatment required for benefit (Figure 2). We also incorporated medication-specific factors from Scott’s framework for minimizing inappropriate medication use, such as drug-specific safety profiles and drug-drug and drug-disease interactions. Finally, patient preferences were viewed as a key component that informs final deprescribing actions by identifying medications the patient is willing to deprescribe (e.g., due to lack of efficacy, poor compliance, side effects, or cost burden) as well as potential barriers to deprescribing (e.g., concerns about worsening of symptoms). Specifically, our goal was to identify opportunities for deprescribing wherein clinical evidence aligned with patient preferences.

### **Conceptual Model**

**Figure 2. Deprescribing Framework**

The intervention has five steps after the initial medication history is collected during baseline assessments. Each step is described in detail below, and the Figure 3 shows the order of the intervention. While patients randomized to the intervention group receive this protocol, patients randomized to the control group receive usual care from the hospital and PAC treatment teams.

### Pre-Review (Target Medications for Deprescribing)

[figure not shown]
Following the baseline patient/surrogate interview, a study clinical reviewer (pharmacist, geriatric nurse practitioner, or physician) receives the reconciled total enrollment medication list. Using medical record data only such as the history and physical, lab values, physician notes, etc., reviewers will first identify a Medication – Indication pairing for each medication (i.e., clinical reviewers try to establish an indication diagnosis or symptom which the medication treats). If an indication does not exist, “no indication indicated” is specified. For each medication recommended for deprescribing, the reviewer chooses one of the following actions: (1) Stop prior to hospital discharge without need for monitoring; (2) Stop prior to hospital discharge with symptoms/physiologic monitoring; (3) Stop at specified time point following hospital discharge; (4) Reduce over time with monitoring until medication is stopped; (5) Reduce to lower dose without need for monitoring; (6) Reduce to lower dose with symptoms /physiologic monitoring. Then the clinician selects a de-prescribing rationale, and they may select more than one rationale (i.e., choose all applicable rationales) from Table 2.

All medications, both prescription and OTC including vitamins and herbal supplements, are reviewed for potential deprescribing. Select medication classes will not be under consideration for active deprescribing, which include the following:

- Anti-rejection medications for organ/ bone-marrow transplantation
- Chemotherapeutic medications for the treatment of known solid organ or hematologic malignancy.

The above medications may be deprescribed during the study period; however, it would solely be under the direction and recommendation of the primary treatment team or primary prescriber of the medication.

**Figure 3. Deprescribing Protocol**

**Table 2. Deprescribing Rationale**

A. No indication for medication / Indication not clear	F. High risk medication based on:
B. Wrong dose or directions for medication	1. Potential drug-drug interaction
C. Inappropriate for current indication due to:	2. Potential drug-disease interaction (e.g. associated with geriatric syndrome)
1. Indication has resolved	3. On Explicit list of PIMs (i.e., Beer’s list  , STOPP list  , and/or RASP list  )
2. Patient is below treatment threshold	G. Medications are inconsistent with goals of care
3. Treating guidelines have changed, medication no longer indicated	H. Risk > benefit given patients limited life expectancy
4. Wrong Indication for medication	I. Evidence of poor adherence or high risk of poor adherence (directions impractical, high cost)
D. Medication is ineffective as evidenced by no change in symptom or condition	J. Medication currently indicated, however is time-limited and expect indication to resolve
E. Duplicate medication for same indication	

Although any rationale may be appropriate for deprescribing medications, clinician-reviewers will establish a priority level of 1 (low) to 10 (high) for discussing deprescribing recommendations. Priority will take into consideration the potential harm of the medication and their relation and potential effect on geriatric syndromes. Deprescribing prioritization will be performed for several reasons. First, in some circumstances, it may be inappropriate to deprescribe multiple medications simultaneously; thus, prioritization may guide the deprescribing

order. Second, the above rationales may not have equal influence on deprescribing decisions and prioritization provides an opportunity to weigh the potential value.

## Incorporate Patient Preferences

Following medication targeting (Figure 3. 2a) intervention participants or their surrogates receive a structured interview by the intervention pharmacist (PharmD) or nurse practitioner (NP) to elicit their preferences regarding medications identified for deprescribing. Surrogates are included in the conversation if the patient's cognitive deficits preclude their ability to fully participate, if the patient prefers to have the surrogate involved in decision making, or if the surrogate has a role in the patient's medication management. The following is assessed for each targeted medication: medication adherence, possible side effects, perceived benefit (or harm) of the medication, cost, and agreement/ disagreement to stopping or reducing the medication. As part of this interview the PharmD or NP may need to provide patient education about individual medications (e.g., side effects, risk-benefit, current evidence) and address any questions or concerns before asking if the patient agrees to deprescribe. If the patient raises a concern about a medication which the study team did not target for deprescribing, the PharmD or NP should still address these concerns and note them in communications with the treatment team. Finally, if a patient agrees to deprescribe a medication for which they have refills, the PharmD or NP informs them that we will be canceling the refills if their provider agrees.

Study clinicians take field notes during the interview in which they detail the patient's general comments about medications and prescribers as well as the rationale for the patient's agreement/disagreement with each deprescribing recommendation. After the interview these comments are coded into pre-set barriers and enablers (e.g., appropriateness, fear, process, influences, pragmatic, and dislike) from an established framework. Patient/surrogate comments can align with more than one category for each medication and should be coded as such. A second study team member, usually the study coordinator or data manager, independently reviews the interview comments and coded for agreement. If there is disagreement related to categorization, the team discuss the theme assignment until a consensus is reached.

## Outpatient Provider Input

Intervention PharmDs or NPs inform patients and in-hospital providers of our intent to engage primary prescribers (Figure 3. 2c) in the deprescribing decisions and ensure they have the final medication list at the time of PAC discharge to incorporate into their medical records for continued medication management. The goal of these conversations is to obtain provider feedback about the proposed changes and facilitate medication updates in the medical record. Additionally, these conversations will hopefully lead to sustained deprescribing by engaging the primary provider early in the process.

Study team clinicians can contact VUMC providers through the EMR messaging service or by paging their clinic. Outside providers are engaged via telephone. In either case, the study clinician provides a brief description of the study, the medication for deprescribing and the rationale, and finally explains the patient's willingness to deprescribe. Much like the patient preference interview, the study PharmD or NP documents the original prescriber's agreement/disagreement and rationale for their decision. These field notes are coded into pre-set barrier and enabler categories (e.g., inertia, self-efficacy, feasibility) from a published framework.

## Inpatient Provider Input

The inpatient treatment team is responsible for the final deprescribing actions of the hospital phase of the intervention. The study team PharmD pages the treatment team at enrollment to notify them that the study team will contact them to provide medication recommendations. After contacting outpatient providers, the study PharmD or NP contacts the inpatient team and explains the recommendations and rationales (Figure 3. 2c). Again agreement/disagreement and provider reasoning are documented and classified in the same manner as with outpatient providers.

## Final Hospital Deprescribing Actions

The final in-hospital phase of the deprescribing protocol requires that the study PharmD or NP assimilate the data from all three phases (Figure 3. 2a, 2b, 2c) to finalize deprescribing actions. Deprescribing can begin at any time after randomization and following step 2a – 2c. All deprescribing actions are executed by the inpatient treatment team using recommendations from the study PharmD or NP. Recommendations include input from the intervention team, patient, inpatient treatment team, and the original prescriber(s) when available.

We anticipate that there will be disagreement between clinical reviewers, inpatient teams, primary prescribers and patients. The incidence and nature of the disagreement will be monitored closely. In anticipation of disagreement the following guidelines will be in place. First, deprescribing of pre-hospital medications will not be recommended to the treatment team (acute or post-acute) without patient agreement. Deprescribing of medications will be recommended against a patient's preferences when there is a clear indication of imminent safety threats as determined by the intervention pharmacist / NP, inpatient clinical team, or primary prescriber. Otherwise, we will first counsel the patient regarding the rationale for the deprescribing recommendation and seek consensus. If disagreement continues, we will monitor the medication throughout the intervention phase for side effects. In addition, we will highlight this medication at discharge for follow-up by the primary prescriber. All final deprescribing actions will be carried out by the inpatient treatment team.

## PAC Handover and Ongoing Deprescribing at PAC Facility

Within 24-hours of transition to PAC, a study pharmacist or NP has a phone conversation with a designated PAC provider with prescribing authority (NP or physician) to review the Transfer Medication List, highlight deprescribed medications and the need for medication-specific monitoring. In addition, all medications recommended for deprescribing may not be stopped prior to hospital discharge in the interest of first monitoring symptoms and ensuring safety or due to delayed contact and input from the outpatient prescriber. Medications for additional deprescribing at the PAC may be highlighted during this initial handover and discussed again in weekly follow-up calls while the patient remains in PAC (Phase 3).

Following PAC handover, we initiate a weekly conversation via telephone with the designated PAC provider to review intervention participants' medication administration record (MAR) and any drug withdrawal events. Reasons for modifying the Transfer Medication List during the PAC stay will be discussed and intervened upon as necessary. The intervention also will continue for participants readmitted to VUMC directly from PAC (estimated 20%) and continue upon transfer back to the PAC. The study PharmD or NP may also continue to communicate with the original prescriber/ outpatient provider during the PAC stay to confirm their agreement with medication changes. At the time of discharge from the PAC facility, a final reconciled medication list will be sent to the patient's primary outpatient providers along with suggestions for continued medication management and deprescribing as well as any explanations for other medication changes made.

For analytical and feasibility purposes, the intervention ends at the point of discharge to home. If a patient discharges to home instead of a partner PAC facility, they will be withdrawn from the study and only considered to have one phase of the intervention. For safety reasons, the study team provides their outpatient provider with the final discharge medication list highlighting any symptom monitoring required.

## **SAFETY MONITORING AND ASSESSMENTS**

We have established a system to report and track adverse events (AEs) including adverse drug withdrawal events (ADWEs), serious adverse events (SAEs), and Suspected Unexpected Serious Adverse Reaction (SUSARs). In this study, an AE is defined as any unplanned healthcare utilization or unexpected death (i.e., patient not receiving hospice services at time of death). These AEs are considered SAEs if they include any untoward medical outcome that results in the following: inpatient hospitalization or prolongation of existing hospitalization, life threatening

condition with immediate risk of loss of life (including escalation of hospital care to Intensive Care Unit), or unexpected death. A SUSAR is an SAE that is suspected to be secondary to the drug withdrawal and is unexpected. Study personnel will monitor the safety of subjects and follow them until the event resolves or is explained.

## Methods and Timing for Assessing, Recording, and Analyzing Safety Parameters

### Notification of Unplanned Healthcare Utilizations and Deaths

Unplanned healthcare utilization (intensive care unit transfers, emergency department visits and/or hospitalizations) and deaths are monitored throughout all study phases for each participant. Both the study coordinator and the data manager have access to a study patient panel in the electronic health record. As such, any time a participant is admitted to the VUMC Emergency Room, VUMC Inpatient Services, or the participant's medical record is updated to indicate death, the coordinator and data manager receive a notification. To determine if a participant had an unplanned healthcare utilization at an outside hospital (OSH), the participants are asked at each follow-up time point if they have been to an emergency room or had an inpatient stay, and if so, at what facility. The study coordinator and data manager are responsible for requesting medical records from OSHs (and SNFs) relevant to the utilization.

### Review of Unplanned Healthcare Utilizations and Deaths

Any unplanned healthcare utilization (e.g., hospitalization, ER visit) or unplanned death (e.g., patient not receiving hospice care) is reviewed to determine if it was an adverse event that was serious, related to the study, and unexpected (SUSAR). Once all necessary records have been obtained and collated by the study coordinator, the case is assigned to a physician co-investigator (adjudicator) blinded to group assignment. Through a structured review protocol of all relevant medical records from both within and outside of VUMC (e.g., admission medication lists, discharge lists, SNF MAR, available outpatient notes, laboratory results, etc.), the adjudicator uses an established methodology to determine the presence of serious medication errors.

Clinician-adjudicators will decide whether the unplanned healthcare utilization is related to medication withdrawal (i.e., ADWE) using the 10-question Drug Withdrawal Probability Scale, a scale based on the Naranjo algorithm, which is a validated scoring system to assess causality of adverse drug events. ADWE will be coded as definite (>8), probable (5-8), possible (1-4), and doubtful (<1). For all ADWEs, clinician-adjudicators will then determine whether it was avoidable by any change in management. Differences between adjudicators will be resolved through discussion or, when necessary, the involvement of a third adjudicator.

After review by the clinician-adjudicator, the case is sent to the Principal Investigator to review. Both the PI and a co-investigator appointed by the DSMB review to determine if the event was unexpected and/or study related. Should the event be determined as SUSAR (serious, unexpected, and study related) it will be reported as such to the DSMB and IRB as outlined below.

## Serious Adverse Events and Reporting Procedures

To ensure proper and timely reporting of adverse events, the following communication plan is utilized. The project coordinator is responsible for reporting adverse events to the NIA/DSMB and the IRB in a timely manner and in accordance with each group's guidelines. Our procedures are as follows:

1. **NIA/DSMB:** The NIA project officer and chair of the DSMB will receive a monthly listing of all adverse events, including a brief synopsis, by type of event and group. The NIA project officer will receive a semi-annual report with enrollment updates, attrition numbers, and adverse events data (i.e., group comparisons, individual case listings), which he then distributes to DSMB members in advance of the semi-annual meeting. The project officer will be notified of all participant deaths, regardless of study relatedness, within 48 hours of PI notification of the death.
2. **IRB:** PIs will notify the IRB of any Serious, Unexpected, Study Related Adverse Event within 7 days of PI notification of the event. Any noncompliance with the IRB approved protocol that increases the risk or

affects the patient's rights, safety, or welfare also need to be reported within one week. At the time of the IRB annual continuing review, the IRB receives copies of the reports generated from DSMB meetings. If the DSMB meeting report identifies a new risk to or a change in the risk benefit ratio, the IRB will be notified within 10 days of PIs receipt of the report.

## STATISTICAL CONSIDERATIONS

### Sample Size and Randomization

Figure 1 illustrates the flow of participants through the study and estimated total sample sizes during each study phase based on prior data. The overall effectiveness of the intervention will be evaluated based on the primary outcome measure, which is total medication count. Based on current enrollment rate, we estimate that approximately 144 patients per year will enroll in the study, or 576 across all four years of enrollment. Among those, we estimate that 27.5% will either die or otherwise be lost from the study prior to the 90-day post PAC discharge follow up period. Thus, across all four years of enrollment, an estimated 420 patients will contribute measurements at 90 days. Although 567 is the expected total enrollment, we conservatively use 420 to estimate the statistical power associated with the assessment of overall effectiveness (i.e., overall completion rate) rather than enrollment rate, to account for estimated attrition across all study phases.

Preliminary data is available for the effect of deprescribing on the reduction in the counts of total medications. Our pilot intervention (N=40) was associated with roughly a 50% reduction in the count of total medications from enrollment to hospital discharge, whereas a roughly 25% reduction was observed in the control group receiving routine hospital care. Using these preliminary data and mixed-effects Poisson regression methods, we implemented a simulation-based power analysis wherein we assumed that this effect would be attenuated by 20% at SNF discharge, and again by 20% at the 90-day follow up. Using a sample size of 420, there is greater than 95% power to detect a 50% versus 25% reduction in total medications. There is approximately 90% power to detect a 30% versus 25% reduction in total medications, and 80% power to detect a 27.5% versus 25% reduction in total medications. Thus, the target sample size provides some protection against effects that are substantially smaller than that observed in our preliminary data.

Participants will be randomized in a 1:1 ratio using permuted blocks of two or four, where the size for each block is selected uniformly at random. This type of randomization ensures balance across the intervention and control groups after every second or fourth randomization (depending on the size of the current block). This randomization scheme will be generated by computer using the Mersenne-Twister pseudo random number.

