### Study Population and Sample Size

The eligible patient population is patients age  $\geq 50$  with polypharmacy as defined by  $\geq 5$  medications based on the pre-hospital admission; able to self-consent or has a proxy; home residence within the nine-county radius of VUMC; does not reside in long-term care and is not hospice eligible. All eligible patients will be approached for consent. We anticipate enrolling approximately 144 patients per year, or 576 across all four years of enrollment. Among those, we estimate that 27.5% will either die or become unreachable prior to 90-day follow up. Thus, across all four years of enrollment, 420 patients will contribute measurements at 90 days. Although 567 is the expected enrollment, we conservatively use 420 to estimate the statistical power

associated with our hypotheses based on overall completion rate, rather than enrollment rate, to account for attrition.

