## **STUDY DESIGN**

The study is a 5-year, randomized controlled clinical intervention trial at a singular academic medical center.

Primary Outcomes are change in total number of medications including the number of potentially inappropriate medications, number of medications associated with geriatric syndromes, and medications that contribute to anticholinergic and sedative drug burden.

Secondary Outcome is the impact of deprescribing on prevalence and severity of geriatric syndromes, medication adherence, and functional health status.

Eligible patient population is aged 50 years or older, experiencing polypharmacy as defined by 5 or more home medications, and hospitalized at VUMC with a referral to partner post-acute care facility.

Exclusion criteria include limited life expectancy (less than 6 months), non-English speaking, no telephone, homeless or incarcerated, enrolled in another drug trial, and expected to discharge from VUMC in less than 48 hours.

The primary study setting is Vanderbilt University Medical Center (VUMC), a private, non-profit, tertiary care teaching organization located in Nashville, Tennessee. The medical center is a principal referral center for physicians and patients throughout the Southeast, and it serves a diverse population in terms of income, geography, and education level. We will work with patients discharged to 20 SNFs and 2 IPRs within a nine-county radius of Nashville. The target PACs are all for-profit and comparable to PACs in the middle TN area based on publicly reported staffing and quality indicators ([www.medicare.gov](http://www.medicare.gov)).

The timeline for the study is 5 years with enrollment beginning in March 2017 and enrollment closing at the end of October 2020.

The Shed-MEDS intervention is a multistep deprescribing protocol which considers patient and disease factors, life expectancy, goals of care, and appropriate treatment targets. Medication-specific factors such as drug-drug interactions, drug-disease interactions, and drug-specific safety profiles are also incorporated. Finally, patient preferences and primary prescriber input are key to final deprescribing actions by identifying the medications patients are willing to discontinue and seeking their primary prescriber's agreement. In this intervention, deprescribing is defined as either stopping a medication or reducing the dose/frequency of a medication.

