## Outcomes

Hypotheses 1a-1b: The effect of the intervention on the total number of medications, PIMs, and medications associated with geriatric syndromes at hospital discharge, SNF discharge, and at 90-days following SNF discharge will be assessed using mixed effects Poisson regression, allowing for overdispersion (more or less variability than is expected under the Poisson regression model), and adjusting for measurement time point (as a categorical covariate) and the total number of medications at participant enrollment. The within-subject correlation among repeated measurements will be modeled using a random intercept term, indexed by subject. The intervention effect at each time point will be summarized using a Wald-type 95% confidence interval. Statistical significance will be indicated if the 95% confidence interval excludes the value zero (i.e., the Poisson regression intervention effect under the null hypothesis). Model fit will be assessed by examining the associated Pearson residuals and using other graphical methods. Alternative regression techniques may be used in the case of poor fit, for example, negative-binomial regression.

Hypothesis 1c: The effect of intervention on the anticholinergic and sedative medication drug burden scores at hospital discharge, SNF discharge, and 90-days following SNF discharge will be assessed using linear mixed effects regression, adjusting for measurement time point, and using a random intercept term indexed by subject. Intervention effects will be summarized using 95% confidence intervals. Model fit will be assessed using residual diagnostics and graphical methods. Due to the constrained nature of the score values (0-1 for anticholinergic and sedative drug burden scores), an alternative method may be required, such a ‘beta’ regression, which is suitable when such scores frequently occur at a boundary (0 or 1).

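### The stated powers of about 90% (30% vs 25% reduction) and 80% (27.5% vs 25%) at N=420 cannot both hold for the same test

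*Combined protocol and SAP*

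**What the plan says.** The section Sample Size and Randomization names total medication count as the measure of overall effectiveness and bases power on 420 participants with 90-day data. The method is a simulation with mixed-effects Poisson regression. The pilot effect is a reduction of roughly 50% against 25%, and "we implemented a simulation-based power analysis wherein we assumed that this effect would be attenuated by 20% at SNF discharge", with a further 20% at 90 days.

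Three powers follow. For the pilot-sized effect: "Using a sample size of 420, there is greater than 95% power to detect a 50% versus 25% reduction in total medications". For smaller effects: "There is approximately 90% power to detect a 30% versus 25% reduction in total medications, and 80% power to detect a 27.5% versus 25% reduction". The section concludes that the sample size gives some protection against effects well below the pilot's. It names no separate test, visit or alpha for any of the three.

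The Outcomes section (Hypotheses 1a-1b) gives the analysis: "The intervention effect at each time point will be summarized using a Wald-type 95% confidence interval" and "Statistical significance will be indicated if the 95% confidence interval excludes the value zero". That implies two-sided 0.05.

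**The concern.** Going from 30% to 27.5%, against 25% in the control arm, halves the treatment difference. With N, control arm, model and test unchanged, the expected test statistic is roughly halved too. Power near 90% would then fall steeply, not by ten points.

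The 80% figure is the plan's claim for its smallest effect. If it is the wrong one, a reader of a null or small result would believe that a 2.5-point difference was reliably detectable when the chance of detecting it was between one in three and one in two.

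**Working it through.** **Inputs.** From Sample Size and Randomization: N = 420, control reduction 25%, intervention reductions 30% and 27.5%, powers 90% and 80%. From Outcomes: Wald 95% interval, so z = 1.960. Baseline mean, random-intercept variance and dispersion are not given. They are not needed to compare the two powers, because they act almost equally on both scenarios and so cancel.

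**Step 1, effect sizes (log rate ratios).**
- 30% vs 25%: ln(0.75/0.70) = 0.0690
- 27.5% vs 25%: ln(0.75/0.725) = 0.0339
- Ratio: 2.035

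**Step 2, the ratio the two powers allow.** Power = Φ(effect/SE − 1.960). So 90% needs effect/SE = 1.960 + 1.282 = 3.242, and 80% needs 1.960 + 0.842 = 2.802. With a common SE the allowed ratio is 3.242/2.802 = 1.157. Read generously as 95% and 75%, it is (1.960 + 1.645)/(1.960 + 0.674) = 1.368. Neither is near 2.035.

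**Step 3, take 90% as correct.** SE = 0.0690/3.242 = 0.0213. Power for 27.5% vs 25% = Φ(0.0339/0.0213 − 1.960) = 0.357. If the 90% stands for 85% or 95%, the result is 0.313 or 0.425. The curve against 25% is:

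| Intervention reduction | 27.5% | 28% | 28.5% | 29% | 29.5% | 30% |
|---|---|---|---|---|---|---|
| Power | 36% | 48% | 61% | 73% | 83% | 90% |

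Power of 80% is reached at 1 − 0.75·exp(−0.0213 × 2.802) = 29.3% vs 25%.

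**Step 4, take 80% as correct.** SE = 0.0339/2.802 = 0.0121. Power for 30% vs 25% is 0.9999 (0.9997 if the 80% stands for 75%). Power of 90% is already reached at 1 − 0.75·exp(−0.0121 × 3.242) = 27.9% vs 25%.

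The two implied SEs differ by a factor of 1.76, so the variances differ 3.1-fold. If the 90% holds, 80% power for 27.5% vs 25% would need about 420 × 3.1 ≈ 1,300 completers.

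**Step 5, other readings of the test.** Each is scaled so that 30% vs 25% has 90% power. The multi-visit rows assume three correlated normal statistics with equal SE and correlations from 0 to 0.9. The 20% attenuation is applied to the difference, to both arms, to the log ratio, or not at all.

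| Reading | Power for 27.5% vs 25% | If the 90% means 85-95% |
|---|---|---|
| Single test, one-sided 0.05 | 42% | 37-49% |
| Significant at any of three visits | 37-44% | 33-51% |
| Joint test, 2 or 3 df | 33% or 31% | not computed |
| Significant at all three visits | 10-35% | not computed |

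Taking 80% as correct instead, power for 30% vs 25% exceeds 99.9% on every one of these readings.

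**Step 6, could another alpha reconcile them?** Both powers hold for one test only if c + 1.282 = 2.035(c + 0.842), which gives c = −0.417. A one-sided test with that critical value rejects about 66% of the time under the null.

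**Step 7, simulation check.** Random-intercept Poisson counts were simulated with 210 per arm, three visits, a pooled effect and an assumed baseline of 25 medications (the pilot's 12.6 deprescribed, divided by roughly 50%). Power for 30% and 27.5% vs 25% was 99% and 54% with subject SD 0, 93% and 40% with SD 0.1, and 64% and 23% with SD 0.2. No setting tried came near 90% and 80% together.

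**The case against.** The strongest reply is that the simulation's code, variances and tested contrast are not shown, so calling the pair impossible depends on assumptions about it. One reading does bring the figures close: apply the 20% attenuation to the intervention arm's reduction only and hold control at 25%. Scaled to 90% at 30% vs 25%, power for 27.5% vs 25% at any visit is then 84% at correlation 0.9 and 89% at 0.5. But on that reading the intervention reduction falls from 30% to 24% and then 19.2%, below the control's 25%. Most of those rejections are in the wrong direction. Counting only rejections for a greater reduction, and setting that power to 90% at 30% vs 25%, gives 36% again. It is not power to detect the stated reduction.

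A second reply is that little rests on the disputed figure, and this largely stands. The 420 comes from expected enrolment and attrition, not from the 2.5-point effect. Power for the pilot-sized effect is untouched. On the branch where the 80% is right, the plan only understates its power for 30% vs 25%. It also stands that the two powers might refer to different tests or visits, but the text does not say so.

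**Conclusion.** The two powers contradict each other. For a single two-sided 0.05 test, 90% at 30% vs 25% implies about 36% at 27.5% vs 25% (31-43% allowing for rounding), and 80% at 27.5% vs 25% implies more than 99.9% at 30% vs 25%. This assumes the same test, N and variance for both figures, as the text implies, and an effect that favours the intervention at every visit. It does not depend on the undisclosed baseline count or variance components. Which figure is wrong cannot be settled from the documents. The conclusion about some protection against smaller effects survives on either branch; on the worse one, 80% power is at about 29.3% vs 25%.

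Two minor inconsistencies sit beside it. Expected enrolment is given as 576 ("We anticipate enrolling approximately 144 patients per year, or 576 across all four years of enrollment", and 144 × 4 = 576) but also as 567 ("Although 567 is the expected total enrollment, we conservatively use 420 to estimate the statistical power"). The four years of enrolment do not match the Study Design section, "enrollment beginning in March 2017 and enrollment closing at the end of October 2020", which is 44 months. Neither affects the comparison of the two powers.

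**What to change.** Rerun the existing simulation. State the test or time point that the power refers to, alpha, baseline mean count, random-intercept variance and dispersion, and how the attenuation is applied. Restate the two small-effect powers so that they agree, or correct the effect size if one was mistyped. If they refer to different tests or visits, say so.

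Use one expected enrolment figure in Study Population and Sample Size and in Sample Size and Randomization, and reconcile the four years with the enrolment dates.

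The cost is one simulation rerun and some corrected wording. The stated power for the smallest effect may become less favourable.
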